A Multi-center Clinical Study on the Efficacy and Safety of Kuntai Capsule Alone and in Combination With Hormones in the Treatment of Early-onset Hypoovarian Function

NCT05021094

Date: August 4, 2021

Research Proposal Summary

| Scheme number | HYKT18017S |
|------------------------|---|
| Scheme name | A Multi-center Clinical Study on the Efficacy and Safety of Kuntai Capsule Alone and in |
| | Combination With Hormones in the Treatment of Early-onset Hypoovarian Function |
| Version number/date | Version 2.1 , June 18 , 2021 |
| sponsor | Shanghai Haitian Pharmaceutical Technology Development Co., Ltd. |
| Clinical trial staging | Post-marketing clinical re-evaluation |
| test drug | Heyan Kuntai Capsules [®] (Z20000083), each0.5g, was produced by Guiyang Xintian Pharmaceutical Co., Ltd. |
| Indications | POI (including subclinical stage) |
| Test purposes | To evaluate [®] the efficacy and safety of Heyan Kuntai Capsules alone or in combination with hormone therapy in patients with POI (including subclinical stage) in improving ovarian function . |
| Research design | Prospective, multicenter, randomized, controlled clinical trial design |
| total number | It is planned to complete 120 cases (considering the 20% dropout rate, at least 150 cases need to be |
| of cases | enrolled) |
| number of research | 6_ |

| centers | |
|--------------|---|
| Study period | 24 months |
| research | Diagnostic criteria : |
| object | The diagnostic criteria for premature ovarian insufficiency (POI) refer to the "2017 Chinese |
| | Expert Consensus on Clinical Diagnosis and Treatment of Premature Ovarian Insufficiency" and |
| | "2016 Expert Consensus on Hormone Supplementation Therapy for Premature Ovarian |
| | Insufficiency"; including: (1) Age <40 years old; (2) oligomenorrhea or amenorrhea for at least 4 |
| | months; (3) at least 2 times serum basal follicle-stimulating hormone (FSH) > 25 IU/L (interval > 4 |
| | weeks). Subclinical POI: FSH level is 15~25 IU/L, which is a high-risk group. |
| | The diagnostic criteria for premature ovarian failure (POF) refer to the "2017 Chinese Expert |
| | Consensus on Clinical Diagnosis and Treatment of Premature Ovarian Insufficiency", which refers |
| | to amenorrhea, FSH>40IU/L, and decreased estrogen levels before the age of 40, accompanied by |
| | varying degrees of perimenopause Stage symptoms are the terminal stage of POI. |
| | standard constrain: |
| | 1. 18 years old ≤ age < 40 years old; |
| | 2. At least two (>4 weeks interval) basal FSH≥15IU/L, with or without oligomenorrhea or |
| | menopause. |
| | 3. Informed consent, voluntary experiment. |
| | Exclusion criteria: |
| | 1. pregnant and lactating patients; |
| | 2. Patients with endometriosis , adenomyosis , endometrial lesions (submucosal fibroids , |
| | endometrial polyps, etc.), uterine fibroids >4cm or hysterectomy; |
| | 3. Patients with known or suspected history of breast cancer and estrogen-dependent |
| | malignancies; |
| | 4. a personal history of venous thromboembolism (VTE) or with a high risk of VTE (including |
| | body mass index > 30 kg/m ² , smoking, family history of thrombophilia); |
| | 5. Porphyria patients; |
| | 6. Patients with serious primary diseases such as cardiovascular, liver, kidney, hematopoietic |
| | system or mental illness; |

- 7. Patients who are participating in other clinical trials or have participated in other clinical trials within the past three months;
- 8. Patients with suspected or real history of alcohol and drug abuse;
- 9. Known allergy to the investigational drug or its components;
- 10. Other patients deemed unsuitable for participation in this trial by the investigator.

Note: Patients who were receiving hormone replacement therapy at the time of recruitment were required to take at least a 3 -month suspension of medication to participate in this trial.

Trial grouping

and medication

1 POI patient

According to the random sequence generated by computer, eligible patients were randomly assigned to Kuntai group, control group and combination group according to 1:1:1.

- (A) Kuntai group (30 cases): Oral Kuntai capsules, 4 capsules at a time, 3 times a day, 28 days as a course of treatment, taking medicine for 3 courses;
- (B) Control group (30 cases): the sequential regimen of estrogen and progesterone was used, and the drug was estradiol tablets/estradiol dydrogesterone tablets (fenmetone), and red tablets (estradiol, 2 mg/d), and gray tablets (estradiol, 2 mg/d, dydrogesterone, 10 mg/d) were taken for the next 14 days, 28 days as a course of treatment, and three courses of medication were taken.
- (C) Combination group (30 cases): On the basis of hormone therapy, Kuntai Capsules were added, and the dose was the same as that of Kuntai group and hormone group for 3 months.
- 2. Patients with POI in subclinical stage: self-control before and after experiment group (30 cases): Oral Kuntai capsules, 4 capsules at a time, 3 times a day, 28 days as a course of treatment, taking medicine for 3 courses of treatment.

Treatment and

follow-up

- 1. Course of treatment: 28 days as a course of treatment, taking medicine for 3 courses of treatment
- 2. Visit points: before treatment (stage V $_{0}$, screening period, days -35 $\rm to~0$), baseline period (day
- 0), after 3 months of treatment (stage V_1 , days 84 to 105), drug withdrawal 3 months later (V_2 stage, 168-210 days) and 6 months after drug withdrawal (V_3 stage, 252-315 days).

Specific inspection items include:

- 1. The patient 's hormone levels (basal FSH, LH, E₂) were detected in V₀, V₁, and V₂ stages;
- 2 Anti-Müllerian hormone (AMH) was detected in patients at V 0 and V 1 stages;
- 3 The patients underwent B-ultrasound at V 0 and V 1 stage to monitor the follicular development,

| | record the number of antral follicles (AFC), ovarian hemodynamic parameters (PSV, EDV, S/D, RI |
|----------------|---|
| | and PI); |
| | 4. Modified Kupperman score was performed in V $_{0}$, V $_{1}$ and V $_{2}$ stage; |
| | 5 Pregnancy was recorded at the V $_2$ outpatient follow-up for patients with reproductive needs; |
| | 6 patients at V $_{0}$ and V $_{1}$ to detect blood routine (RBC, WBC, PLT, HGB) , liver function (ALT, |
| | AST) and renal function (BUN, Cr), and recorded adverse events. |
| | |
| | Note: |
| | 1 Basal follicle-stimulating hormone (FSH) \geq 15IU/L at first visit in patient V0, and if other |
| | inclusion criteria are met, if the patient has a history of testing with a baseline FSH ≥ 15 IU/L in |
| | the past (interval> 4 weeks), he or she can be included in this study and drug therapy can be |
| | started; (Interval > 4 weeks) If the basic FSH \geq 15 IU/L has not been diagnosed, the patient is |
| | required to visit the hospital again after 4 weeks. If the basic FSH is still \geq 15 IU/L, they can be |
| | included in this study and drug therapy can be started. |
| | 2 For patients with regular menstrual periods, the basal FSH and antral follicle count (AFC) |
| | should be followed up on the 2nd to 4th day of the menstrual cycle. If the patient has menstrual |
| | cramps after the follow-up and has not exceeded the visit window, they are required to re-examine |
| | on the 2nd to 4th day of the menstrual cycle and record the examination data. |
| study endpoint | Primary endpoint : FSH, modified Kupperman score |
| | Secondary endpoints : |
| | (1) FSH/LH, LH, E ₂ ; (2) Antral follicle count (AFC); (3) Anti- Müllerian hormone (AMH); (4) |
| | Proportion of patients with normal menstruation; (5) Ovarian hemodynamics parameters (PSV, |
| | EDV, S/D, RI and PI); (6) Clinical pregnancy rate (patients with reproductive needs). |
| security | 1 Blood routine (RBC, WBC, PLT, HGB), liver function (ALT, AST) and renal function (BUN, |
| indicators | Cr); |
| | 2 Patient adverse events were recorded. |

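### Do the inclusion criteria admit women whom neither cohort definition covers, so that an assignment rule must be added?

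*Protocol*

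**What the plan says.** The relevant text is in the Protocol's research object row, the trial grouping section and the notes under treatment and follow-up.

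- **Entry.** Inclusion item 2 asks for "At least two (>4 weeks interval) basal FSH≥15IU/L, with or without oligomenorrhea or" menopause. There is no upper FSH limit.
- **POI.** Besides age under 40, the diagnostic criteria list "2) oligomenorrhea or amenorrhea for at least 4" months and "at least 2 times serum basal follicle-stimulating hormone (FSH) > 25 IU/L", the values more than 4 weeks apart.
- **Subclinical POI.** "Subclinical POI: FSH level is 15~25 IU/L, which is a high-risk group". The text does not say how many values must lie in that range.
- **Premature ovarian failure (POF).** The definition points "to amenorrhea, FSH>40IU/L, and decreased estrogen levels before the age of 40, accompanied by" symptoms typical of the menopausal transition. The Protocol treats POF as the end stage of POI and gives no duration for the amenorrhea.
- **Purpose.** The drug is to be evaluated "in patients with POI (including subclinical stage) in improving ovarian function".
- **Grouping.** POI patients are randomised to three arms of 30. Subclinical patients form one before-after group of 30. No FSH or menstrual rule is repeated here.
- **Note 1.** A second FSH value, past or repeated, need only reach 15 IU/L. The figure 25 does not appear.
- **Note 2.** Tests are timed by cycle day in women with regular periods.

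The SAP does not mention cohort assignment.

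**The concern.** The entry rule is wider than the two diagnoses that decide where a woman goes. Someone who passes screening might match neither definition, or match one only on an interpretation the text does not supply. Cohort is a consequential label in this trial: it separates a randomised comparison from an uncontrolled before-after group. Six centres could place the same woman differently. The two variables left unclear are also outcomes, since FSH is a primary endpoint and normal menstruation a secondary one. At stake is which women each cohort's result describes, above all in the single arm, where no control group absorbs a shift in case mix.

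**Working it through.** **The plan's own figures.** Four groups of 30 give 4 × 30 = 120 completers. With 20% dropout, 120 / (1 − 0.20) = 150, which matches "It is planned to complete 120 cases (considering the 20% dropout rate, at least 150 cases need to be" enrolled. The sample size is consistent and does not bear on the question.

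**Placement of eligible women.** All rows satisfy inclusion item 2. Each is set against the two definitions under three readings: the literal text; item 2 taken to waive the menstrual criterion; and the diagnosis taken as a further entry condition beside the inclusion criteria.

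| FSH values and cycles | Literal | Menstrual criterion waived | Diagnosis also required |
|---|---|---|---|
| Both 15–25, any cycles | Subclinical | Subclinical | Subclinical |
| Both above 25, disturbed for 4 months or more | POI | POI | POI |
| Both above 25, regular cycles | Neither | POI | Not enrolled |
| Both above 25, disturbed for under 4 months | Neither, unless POF | POI | Not enrolled, unless POF |
| One 15–25, one above 25, no further value | Not POI; subclinical only if one value is enough | Same | Enrolled only if one value is enough |

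**Rows three and four.** These women are enrolled without a cohort only if both alternative readings are rejected. Each alternative has support. The diagnostic criteria open the same row as the inclusion criteria, and the indication and the grouping headings use those diagnoses, which suggests that a diagnosis is required. Item 2's indifference to menstrual change is then needed because subclinical POI is defined by FSH alone.

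**What the notes show.** Note 2 is fully explained by subclinical women with regular cycles, so it is not evidence that women with FSH above 25 and regular cycles are expected. Note 1 explains how the second FSH value may be obtained. It omits the exclusion criteria too, and they plainly still apply, so its silence on diagnosis proves little.

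**Row five.** This is open on every reading, but it is narrower than it looks. Both item 2 and the POI definition ask for at least two values. A woman with 20, 30 and 32 IU/L has two values above 25 and meets the FSH part of POI. The gap is limited to women with no further value.

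**Size.** The documents give no FSH or menstrual distribution, so the number affected cannot be derived. The weight of one placement is:

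- single arm: 1/30 = 3.3% of planned completers, or 1/37.5 = 2.7% if the 150 are spread evenly (150/4 = 37.5, an assumption);
- randomised cohort: 1/90 = 1.1%, or 1/112.5 = 0.9% on the same assumption (3 × 37.5 = 112.5).

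These figures would accompany any classification question. They say nothing about how often this one arises or how far a result would move.

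**Effect on the randomised comparison.** Cohort rests on diagnosis, and the random sequence is then applied to the POI patients. A borderline woman who enters that cohort is as likely to go to one arm as to another, so the comparison between arms is not biased.

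**The case for a change.** The strongest case for a change is that the straddling pair survives every reading. Note 1 makes it foreseeable: it accepts a past value of at least 15, sets no limit on that value's age, and lets treatment start without mention of 25. The single arm has no control to absorb a change in case mix, and FSH is both the sorting variable and a primary endpoint. A sentence of protocol wording would cost little.

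Part of this stands. The supplied text does not say which FSH values decide cohort when they fall on both sides of 25, nor whether the menstrual criterion applies to entry. Stating both would make each cohort's population clearer, and the clinical boundary would be the sponsor's to set.

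It does not carry a required change. No effect on either result can be shown, and the randomised arms stay balanced. One obvious remedy, limiting entry to women who meet a written definition, leaves the straddling woman where she was, because whether she meets the subclinical definition is the open question. It is also not established that the data are already in hand: the listed visit examinations include no menstrual history, although normal menstruation is a secondary endpoint. Finally, the Protocol is headed as a summary and refers to two consensus documents for its criteria. A fuller protocol or those sources may hold the rule; the supplied text cannot settle that.

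**Conclusion.** No change to the plan follows. The mismatch in wording is real, but what remains of it is missing detail. Women with FSH above 25 and regular or briefly disturbed cycles are a problem only on a reading that sets aside both natural alternatives. Women whose values straddle 25, with no further value, lack a written rule, and centres would probably sort them by FSH level.

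The consequence is confined to how sharply each cohort's population is described. Its size cannot be estimated from the documents; the only figures available are 1 of 30 (3.3%) and 1 of 90 (1.1%) for a single placement.

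The conclusion rests on two assumptions: that cohort is settled before the random sequence is applied, as the grouping section's layout implies, and that centres sort on FSH in broadly the same way. If centres sorted differently, the case mix of the single arm could vary between them, but the randomised comparison would still hold.

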A Multi-center Clinical Study on the Efficacy and Safety of Kuntai Capsule Alone and in Combination With Hormones in the Treatment of Early-onset Hypoovarian Function

NCT05021094

Date : August 4 , 2021

Statistical analysis

The case observation form completed by the test center was reviewed and returned by the project team of Shanghai Haitian Pharmaceutical Technology Development Co., Ltd., and the data was processed by a statistical analyst. The data in the case report form is entered in two copies, and the database is locked after verification and confirmation. SPSS26.0 software was used for statistical analysis. The full analysis set (FAS) and the per-protocol set (PPS) were used for effectiveness analysis, and the safety data set (SS) was used for safety analysis. Measurement data were expressed as mean \pm standard deviation ($\bar{x} \pm s$), multiple time points were compared by repeated measures analysis of variance, and pairwise comparisons were by Bonferroni test; enumeration data were expressed by the number of cases or percentages, and χ^2 was used.Test for statistical comparison.P<0.05 indicated that the difference was statistically significant.

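### Every woman has two qualifying pre-treatment FSH values, but the plan names no baseline and has no use for the second; as a separate covariate it would add precision to the randomised comparison at almost no cost

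*Protocol*

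**What the plan says.** - **Eligibility (protocol, inclusion item 2).** Each woman needs "At least two (>4 weeks interval) basal FSH≥15IU/L".
- **Two routes to the second value (protocol, Treatment and follow-up, Note 1).** A woman whose first study test qualifies may enter on a past qualifying test, provided the interval exceeds 4 weeks. No maximum age, laboratory or assay is set for that test. A woman without one is "required to visit the hospital again after 4 weeks" and enters if the repeat also qualifies.
- **Schedule (protocol, Treatment and follow-up).** Basal FSH is measured at V0, V1 and V2. V0 is a window from day -35 to day 0, and a day-0 baseline period is listed separately. A woman who is retested can therefore have both readings inside V0.
- **Endpoint (protocol, Study endpoint).** "Primary endpoint : FSH, modified Kupperman score". No change score, time point or baseline is defined.
- **Analysis (SAP, Statistical analysis).** "multiple time points were compared by repeated measures analysis of variance", with Bonferroni pairwise comparisons. There is no baseline covariate and no definition of baseline FSH.

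**The concern.** A basal FSH reading is a noisy measure of a woman's underlying level. Two readings more than 4 weeks apart carry more information about that level than one does, and eligibility already obliges each site to hold both. The plan assigns no role to the second reading, in a trial with about 30 women per randomised arm, where precision on a primary endpoint is scarce. Recovering that information needs no extra patient, visit or sample.

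Separately, the baseline for a retested woman is left to be chosen later. That is missing detail, but it has to be settled before either reading can enter a model.

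**Working it through.** **The plan's own figure.** 120 / (1 - 0.20) = 150 enrolled, and 3 × 30 + 30 = 120 completers. Both reproduce. The documents give no power, effect size, SD or FSH correlation.

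**Inputs.** From the documents: two qualifying values per woman, FSH at V0, V1 and V2, and 30 women per randomised arm. Assumed: unit variance at every reading; correlation r between V0 and a post-treatment value; correlation r' of the other qualifying value with both V0 and the post-treatment value.

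**1. Both values as separate covariates, equal correlations (r' = r).** Residual variance is 1 - r² with V0 alone and 1 - 2r²/(1 + r) with both.

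| r | V0 only | both | further fall | 30 per arm is worth |
|---|---|---|---|---|
| 0.5 | 0.750 | 0.667 | 11% | 30 × 0.750/0.667 ≈ 34 |
| 0.6 | 0.640 | 0.550 | 14% | 30 × 0.640/0.550 ≈ 35 |
| 0.7 | 0.510 | 0.424 | 17% | 30 × 0.510/0.424 ≈ 36 |

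**2. The other value is a weaker past test (r' < r).** With both covariates the residual variance is 1 - (r² + r'² - 2rr'²)/(1 - r'²).

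- r = 0.8, r' = 0.5: 1 - 0.49/0.75 = 0.347, against 0.360. Fall about 4%.
- r = 0.7, r' = 0.5: 1 - 0.39/0.75 = 0.480, against 0.510. Fall about 6%.
- r = 0.7, r' = 0.3: 1 - 0.454/0.91 = 0.501, against 0.510. Fall about 2%.

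**3. Price of the covariate.** With 90 women, three arm means and one V0 slope leave 90 - 3 - 1 = 86 residual degrees of freedom; a second slope leaves 85. The loss of precision from a useless covariate is therefore of the order of 1/85, about 1%.

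**4. Averaging instead.** Change from one baseline has variance 2(1 - r). Change from the mean of two has variance 1 + (1 + r')/2 - r - r'.

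- r' = r: 1.5(1 - r), which is 25% lower at any r.
- r = 0.7, r' = 0.5: 0.55 against 0.60, an 8% fall.
- r = 0.8, r' = 0.5: 0.45 against 0.40, a 12.5% **rise**.

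Averaging helps only when r' > 2r - 1, so at r = 0.8 the past value must correlate above 0.6.

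**5. Effect of the entry limit.** Both readings must pass a threshold, which narrows their spread. In simulation with both held at or above 25 IU/L (assumed SD 20), the covariate gain was 12% with mean 35 and 14% with mean 45 at a pre-selection correlation of 0.7. It was 7% with mean 35 at a correlation of 0.5. The r in step 1 should therefore be read as the correlation among enrolled women.

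**6. Regression to the mean.** In the same simulation with both readings held between 15 and 25 IU/L (assumed mean 18, SD 8, correlation 0.7), the average untreated change was -0.33 IU/L from one reading and -0.33 IU/L from the mean of two. Using both does nothing for this shift.

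**The case against.** - **The documents do not say that one V0 value is analysed and the other dropped.** This stands. A reader might infer it from the single V0 stage in the schedule, but V0 is a window that can hold two readings, and the SAP is one paragraph. What the documents support is that the baseline is undefined and no use of a second value is planned.
- **The past test may be old, from another laboratory, or taken around earlier hormone use.** This stands. Note 1 sets no limits, and women who stopped hormone therapy at least 3 months earlier may enter. It rules out default averaging. It does not rule out a separate covariate, whose weight the data estimate; a poor value then costs about 1% in precision.
- **The second covariate would differ in kind between women: a study retest for some, an outside test for others.** True, and it dilutes the gain. It cannot bias the randomised contrasts, because both readings are needed for eligibility and so precede treatment. Recording the source lets the dilution be examined.
- **Every size rests on assumed correlations.** True. Entry selection also pulls the gain down.
- **Using one pre-treatment value is ordinary practice.** Also true, so this is an improvement on offer and not a fault. It also presupposes moving to a baseline-adjusted model, which the SAP does not now plan.

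**Conclusion.** The point holds as a cheap gain in precision for the randomised POI comparison. Beyond adjusting for V0, the second covariate lowers residual variance by 11% to 17% if all correlations are equal and lie between 0.5 and 0.7. The gain is about 4% to 6%, or less, if the other value is a weaker past test. The mix of women entering by each route is not stated, so the gain in this trial cannot be fixed more closely.

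Three stronger readings are not supported:

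- **That a quarter of the available variance reduction is lost.** The 25% is the fall in variance of a single-visit change score when two equally correlated, equally variable readings are averaged. The share of the available reduction that adjustment for V0 alone misses is (1 - r)/2: 45% at r = 0.1, 25% at r = 0.5 and 15% at r = 0.7. Nor is an FSH change defined as the endpoint.
- **That the randomised comparison is biased or the plan contains an error.** Neither follows from leaving the second reading unused.
- **That using both readings repairs the before-after subclinical cohort.** Both readings were selected by the same limits, so regression to the mean remains.

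**What to change.** For the three randomised POI arms, before the data are analysed:

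1. Define V0 FSH as the last basal value before the first dose.
2. Record on the case report form the value, date and source (study or past test) of the other qualifying reading.
3. Model post-treatment FSH at V1 and V2, with the V0 value and the other qualifying value as two separate baseline covariates, on the same scale as the outcome.
4. Do not use their mean as the default baseline.

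**Cost:** one degree of freedom and one case report form entry, which the site should be able to supply because eligibility depends on it. The case report form is not among the documents, so it may already capture the value. No patient, visit, sample or clinical rule changes.

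### No stratification by POI stage is stated, and normal menstruation and pregnancy are compared by unadjusted chi-square: the test is valid overall, but it loses power and is exposed to chance stage imbalance

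*Protocol*

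**What the plan says.** The diagnostic criteria in the protocol's Research Proposal Summary set the lower edge of POI at "at least 2 times serum basal follicle-stimulating hormone (FSH) > 25 IU/L (interval > 4" weeks). The same row defines POF, which refers "to amenorrhea, FSH>40IU/L, and decreased estrogen levels before the age of 40", and adds that "varying degrees of perimenopause Stage symptoms are the terminal stage of POI". POF is not an exclusion criterion, and the FSH entry criterion has no upper limit.

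Under Trial grouping and medication, subclinical women go to their own single-arm group. For all other POI women the protocol says: "According to the random sequence generated by computer, eligible patients were randomly assigned to Kuntai group, control group and combination group" in a 1:1:1 ratio, with 30 cases per arm. It mentions no stratification factor, blocking or centre scheme.

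The size of the trial is given as: "It is planned to complete 120 cases (considering the 20% dropout rate, at least 150 cases need to be" enrolled).

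The study endpoint row lists the proportion with normal menstruation and the clinical pregnancy rate as secondary endpoints; pregnancy counts only women with reproductive needs. On such data the SAP says "enumeration data were expressed by the number of cases or percentages" and names the chi-square test at P<0.05. It names no covariate or stratified test.

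**The concern.** The protocol treats stage as important at one boundary, by keeping subclinical women out of the randomisation, but does not use the other boundary that it defines. Amenorrhoea is part of the POF definition, so stage is tied to the menstruation endpoint by construction. If outcome differs much by stage, an arm that happens to receive more POF women will tend to look worse whatever its treatment. A plain chi-square cannot take that into account.

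Two things are at stake: a higher error rate in those trials where a large stage gap occurs, and lost power in all of them, because variation explained by stage is left in the comparison.

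**Working it through.** **1. The plan's own figure.** 120 / (1 - 0.20) = 150, as stated. The 30 per arm is therefore a completer target. For the three POI arms, 90 / 0.80 = 112.5, or about 38 randomised per arm if dropout is the same in all four groups.

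**2. Chance of a stage gap of at least 20 points.** The POF share p is not in the documents; I take 20% to 70%. With X_A and X_B independent Binomial(n, p), the chance for one pair is P(|X_A - X_B| >= k). For n = 30, k = 6 (6/30 = 20.0 points). For n = 38, k = 8 (8/38 = 21.1 points; 7/38 = 18.4 falls short, so part of the drop is rounding). The chance for any of three pairs is simulated.

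| POF share | one pair, n = 30 | any pair, n = 30 | one pair, n = 38 | any pair, n = 38 |
|---|---|---|---|---|
| 20% | 7.5% | 17% | 3.1% | 8% |
| 30% or 70% | 12.0% | 27% | 6.0% | 14% |
| 40% or 60% | 14.7% | 31% | 7.8% | 18% |
| 50% | 15.5% | 33% | 8.5% | 20% |

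Fixing the total number of POF women instead gives nearly the same values (highest at n = 38: 8.6% and 21%).

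**3. Size of the shift.** The documents give no rates by stage. If normal menstruation is 10% in POF and 50% otherwise, a 20-point gap moves the difference between arms by 0.20 x (0.50 - 0.10) = 8 points. With half the women in POF the mean rate is 0.30, and the standard error at n = 30 is sqrt(2 x 0.30 x 0.70 / 30) = 11.8 points. With 20% v 40% the shift is 0.20 x 0.20 = 4 points. Both are below one standard error.

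**4. Error and power for normal menstruation.** Simulation: 400,000 two-arm trials per row, two-sided 5%, no continuity correction, assignment not stratified. Power assumes a treatment log-odds ratio of 1.2 in each stage. CMH is the Cochran-Mantel-Haenszel test by stage.

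| rates, POF v other | n | chi-square error, overall | chi-square error, given gap | CMH error, given gap | gain in power from CMH, points |
|---|---|---|---|---|---|
| 10% v 50% | 30 | 4.8-5.0% | 9.5-11.6% | 4.8-5.0% | 4.8-8.3 |
| 10% v 50% | 38 | 4.9-5.1% | 11.5-14.4% | 4.9-5.1% | 5.9-10.1 |
| 20% v 40% | 30 | 4.7-5.0% | 6.0-6.5% | 4.9-5.0% | -0.1 to 1.6 |
| 20% v 40% | 38 | 5.0-5.2% | 6.9-7.6% | 4.8-5.2% | 0.5-1.7 |

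Ranges cover POF shares of 20%, 30%, 50% and 70%. At 10% v 50%, with half the women in POF and n = 30, power goes from 40.9% to 49.2%. The smallest gains in the first two rows (4.8 and 5.9) are at a POF share of 20%; from 30% upwards the gain is 6 to 10 points.

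**5. Pregnancy.** The size of the subset with reproductive needs is not given. At an assumed 10-15 women per arm, a 20-point gap has a 25-50% chance for a given pair (POF share 20-70%). With assumed pregnancy rates of 3% v 15% or 2% v 20%, the shift is only 0.20 x 0.12 = 2.4 or 0.20 x 0.18 = 3.6 points. With half the women in POF, expected events per arm run from 10 x 0.09 = 0.9 to 15 x 0.11 = 1.65. That is too few for chi-square or for a large-sample stratified test.

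**The case against.** The strongest reply is that randomisation has already dealt with this. Chance imbalance is not bias: averaged over all allocations, unadjusted chi-square error is about 5%, and ordinary sampling error already allows for stage. That stands. What remains is the error given a gap in the one trial that is run, and the loss of power.

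Three stronger readings are tempting, and the documents do not support them.

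- A reader might infer that a 20-point gap is likely. It is not: at most about 16% for a given pair, and no more than one in three for any pair. The lower figures at 38 per arm are the relevant ones at allocation.
- A reader might infer that the plan produces a false difference, or that the women are known to be allocated from one undivided list. The shift rests on assumed rates and is below one standard error. The protocol is a summary that is silent on stratification, so the most one can say is that none is stated.
- A reader might extend the point to the primary endpoint FSH through a baseline gap. FSH is measured at V0, V1 and V2, and the SAP uses repeated-measures analysis of variance. If V0 is among the time points, a baseline gap is not in itself a treatment difference.

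It is also fair to say that the documents do not state how strongly stage predicts outcome. They only call POF the terminal stage. If the dependence is weak, little is gained.

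**Conclusion.** The point holds as a modest improvement to the analysis of two secondary endpoints, not as a flaw that invalidates the trial. No stratification or adjustment by stage is specified, although the protocol itself defines the stages and admits the full range of POI.

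Whether the change matters depends on how far outcome differs by stage. With a 40-point difference in normal menstruation, the stratified test removes a conditional error of about 10-15% and adds about 6-10 points of power over most of the range. With a 20-point difference, the conditional error is about 6-7% (7.6% at the extreme) and the gain in power is at most about 2 points. The POF share, the rates by stage, the treatment effect and the size of the pregnancy subset are all assumptions. For pregnancy, sparse events are the larger limitation.

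**What to change.** In the SAP, replace plain chi-square for normal menstruation with a Cochran-Mantel-Haenszel test stratified by V0 stage: the general-association form across the three arms, and the same stratification in pairwise comparisons. Define the stratum in advance, either by the protocol's full POF definition or by FSH above 40 v 25-40 IU/L; the second is simpler to apply. For pregnancy, use an exact stratified test, or report it descriptively if events are too few.

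If randomisation has not begun, also stratify the sequence by the same factor, with permuted blocks, and state the scheme. The two changes belong together: with stage balanced by design, unadjusted chi-square becomes conservative for menstruation (error about 2.0-4.3% at assumed rates of 10-30% in POF v 40-60% otherwise). If randomisation has begun, change the analysis only.

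The cost is a few SAP sentences and, for stratified allocation, one list per stage. No extra patients, visits or tests are needed, since FSH and E2 are measured at V0 and menstrual status is part of the diagnosis. The downside is that stage must be recorded before allocation and the strata are small: at a POF share of 30%, about 0.30 x 112.5 = 34 women in the POF stratum. Crossing stage with the six centres would leave 112.5 / 12, or about 9 women per cell, so stage should not be crossed with centre without thought.
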